PROTOCOL TITLE:

Communication Intervention for Toddlers with Hearing Loss

PRINCIPAL INVESTIGATOR:

[name], CCC-SLP Communication Science and Disorders

CO-INVESTIGATOR:

[name]. Lurie Children's Hospital

VERSION DATE:

1.04.22

Page 1 of 20 Revised: May 25, 2018

1.0 Purpose of the study:

While children with hearing loss (HL) are experiencing greater gains in spoken language than ever before, considerable variability exists and many children with HL continue to have poorer language skills than their hearing peers. Critical to reducing this variability is the identification of: (a) effective early communication interventions for children with HL and (b) child and parent characteristics that influence intervention outcomes (moderators and mediators). However, to date, only the pilot study for this proposed study has directly examined the effects of an early communication intervention for children with HL within the context of a randomized clinical trial. The overarching goals of the proposed study are to: (a) evaluate the effects of teaching parents to use communication support strategies on child communication outcomes and (b) examine parent and child characteristics that moderate and mediate intervention outcomes. The central hypothesis is that systematic parent training will result in greater parental use of communication support strategies, greater child prelinguistic behaviors, and greater child spoken language outcomes. The specific aims include: (a) comparing parent use of communication support strategies and child prelinguistic outcomes between intervention and control groups during and immediately following intervention, (b) examining parent (communicative insightfulness) and child (sensitivity to social contingency; attention to spoken language) moderators of intervention outcomes; (c) comparing parent use of communication support strategies and child spoken language outcomes between intervention and control groups after intervention (from T7 to T24 months); and (d) examining parent (use of communication support strategies) and child (prelinguistic skills) mediators of intervention outcomes. The proposed study will enroll 96 children with mild to profound bilateral hearing loss.

2.0 Background / Literature Review / Rationale for the study:

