Parent Use of Communication Support Strategies	Latent	Parent use of communication support strategies coded from a parent-child interaction	The following measures from the coded parent-child interaction sample: Percentage of intervals in which the adult is	Monthly from 12 to 18 months of age (6 time points between pre and post)	Analysis 1.1: Dependent Analysis 2.1: Dependent Analysis 4.1a: Mediator Analysis 4.1b: Mediator
			communicating within the child's line of sight Percentage of adult communication that is paired with a gesture in the child's line of sight Percentage of intervals in which the adult's play is related and is in close proximity to the child Percentage of child nonverbal actions that are mirrored and mapped Percentage of child communication that is followed by a contingent response Percentage of adult communication that is in response to child communication Percentage of adult communication Percentage of adult communication that contains a child linguistic target Percentage of child communication to which the adult imitates and adds a word	Monthly from 18 to 36 months of age (18 time points between post and follow-up)	Analysis 3.1: Dependent Analysis 4.2a: Mediator Analysis 4.2b: Mediator
Child Prelinguistic Communicative Acts	Latent	Language Sample	Number of child prelinguistic communicative acts coded from the language sample	12 to 18 months of age (6 time points between pre and post)	 Analysis 1.2a: Dependent Analysis 2.2a: Dependent Analysis 2.3a: Dependent Analysis 4.1a: Dependent Analysis 4.3a: Mediator
Child Overall Prelinguistic Skills	Observed	Communication and Symbolic Behavior Scale (CSBS)	Total Scaled Score	At 18 months of age (post)	 Analysis 1.2b: Dependent Analysis 2.2b: Dependent Analysis 2.3b: Dependent Analysis 4.1b: Dependent Analysis 4.3a: Mediator Analysis 4.3b: Mediator
Child spoken words	Latent	MacArthur-Bates Communicative Development Inventory; Language Sample	Total number of Words Said from the MacArthur- Bates Communicative Development Inventory Total number of different spoken word roots from the language sample	18 to 36 months of age (18 time points between post and follow-up)	 Analysis 3.2a: Dependent Analysis 4.2a: Dependent Analysis 4.3a: Dependent
Child overall spoken language	Observed	Preschool Language Scale-5 th Edition	Total Standard Score	At 36 months of age (follow-up)	Analysis 3.2b: DependentAnalysis 4.2b: DependentAnalysis 4.3b: Dependent

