Covariates. Controlling for covariates is an important part of any analysis. While randomization and stratification should remove effects of these variables, additional statistical control curtails potential unhappy randomizations and other threats to internal validity. As such, we will examine differences between experimental conditions for the following variables: non-verbal cognitive skills, degree of hearing loss in the better ear, hearing age, hours of hearing device use, SES, sign exposure in the home, other spoken languages in the home and amount of community-based early intervention therapy services. Should a difference exist at any point in the study, we will include that variable in all statistical analyses.

Multiple testing. Our proposed analyses and rich multivariate data collection will allow us to test hypotheses in multiple ways. Our focus on SEM will allow for complex hypotheses to be tested with a single model, obviating part of the need for multiple testing corrections. However, we will further employ Benjamini-Hochberg corrections⁸⁸ as needed to correct for multiple testing. This procedure is a more sophisticated alternative to traditional Bonferroni corrections that better account for multiple simultaneous significant parameters.

[figure not shown]
Aim 1 Analyses

This aim tests the main effects of the intervention, both on parental use of communication support strategies and on child prelinguistic skills. We predict that: (a) parents in the intervention group will use more communication support strategies during intervention than parents in the control group (analysis 1.1); (b) children in the intervention group will have greater growth in rate of prelinguistic communicative acts between 12 months (pre) and 18 months of age (post) (analysis 1.2a) and greater overall prelinguistic skills at 18 months of age (post) (analysis 1.2b) than children in the control group. We will employ a mix of traditional and advanced statistical methods, balancing simplicity of linear regression and related methods with sophisticated SEMs that handle attrition and missing data and allow for more flexible integration of time-varying covariates.

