Analysis 2.3a. Intervention effects on a latent slope representing growth in child prelinguistic communicative acts from a monthly language sample from 12 months (pre) to 18 months of age (post) will be moderated by child attention to spoken language (orienting time toward speech from a sequential looking preference procedure) at 12 months of age (pre). Like analysis 2.2a, this model will be estimated using SEM due to the latent child growth outcome.

Analysis 2.3b. Intervention effects on observed CSBS Total Scaled scores at 18 months (post) will be moderated by child attention to spoken language (orienting time toward speech from a sequential looking preference procedure) at 12 months of age (pre). Like analysis 2.2b, this analysis will be carried out jointly using regression methods for assumption checking and SEM for robust estimation of final parameters.

Aim 3 Analyses

This aim tests the long-term effects of the intervention, both on parental use of communication support strategies and on child spoken language outcomes. We predict that: (a) parents in the intervention group will use more communication support strategies after intervention than parents in the control group (analysis 3.1); (b) children in the intervention group will have greater growth in spoken words between 18 months (post) and 36 months (follow-up) (analysis 3.2a) and greater overall spoken language outcomes at 36 months of age (follow-up) (analysis 3.2b) than children in the control group. As in Aim 1, we will employ a mix of traditional and advanced statistical methods, balancing simplicity of linear regression and related methods with sophisticated SEMs that handle attrition and missing data and allow for more flexible integration of time-varying covariates.

Aim 3 analytic plan. Analyses for Aim 3 will again utilize SEM for both regression and latent growth curve models, with the same benefits to attrition and estimation. The analyses here largely mirror those in Aim 1, looking at long-term rather than short-term intervention effects.

Analysis 3.1. Intervention will predict the slope factor in a latent growth curve model of overall parent use of communication support strategies, which is a latent variable of parent use of communication support strategies estimated monthly from 18 months (post) to 36 months of age (follow-up). This will utilize the CUFFS method⁸⁹ of estimating growth in latent variables.

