Analysis 3.2a. Intervention will predict the slope factor in a latent growth curve model of child spoken language outcomes (a latent variable of total number of different words said from the MCDI and total number of different spoken words from a language sample) from 18 months (post) to 36 months of age (follow-up). This will be accomplished by including intervention as a predictor in the child spoken word growth curve.

Analysis 3.2b. Intervention will predict PLS-5 Standard Scores at 36 months via multiple regression. We will test PLS-5 Standard Scores controlling for pre-test scores as we did in Analysis 1.2b.

Aim 4 Analyses

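### Aim 3 predicts that treated parents use more strategies after intervention, but Analysis 3.1 names only a slope effect on a curve starting at T7, and that slope does not test amount of use

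*SAP*

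**What the plan says.** Under Aim 3 Analyses, the SAP's first prediction is that "parents in the intervention group will use more communication support strategies after intervention than parents in the control group (analysis 3.1"). The second, for children, is that "children in the intervention group will have greater growth in spoken words between 18 months (post) and 36 months (follow-up) (analysis 3.2a"). The analytic plan then reads: "Analysis 3.1. Intervention will predict the slope factor in a latent growth curve model of overall parent use of communication support strategies", with the curve running from post to follow-up. For parent strategy use, Table 1 gives the occasions as "Monthly from 18 to 36 months of age (18 time points between post and follow-up"). The SAP names no effect on the intercept, on the mean over the window or on the level at follow-up as part of 3.1.

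The Aim 3 analytic plan explains the choice: "The analyses here largely mirror those in Aim 1, looking at long-term rather than short-term intervention effects". The Aim 1 counterpart is that "parents in the intervention group will use more communication support strategies during intervention than parents in the control group (analysis 1.1"), also tested on a slope, but on a curve that starts at baseline.

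Section 1.0 of the protocol words the aim as "comparing parent use of communication support strategies and child spoken language outcomes between intervention and control groups after intervention (from T7 to T24 months"). That wording is neutral between level and trajectory and is not limited to growth. Protocol section 8.0 gives six months of weekly sessions and places T7 immediately after them. The SAP labels the same window by nominal age (18 to 36 months), which does not affect this point.

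**The concern.** A slope test suits Analysis 1.1. Randomised arms have equal expected levels at T0, so with linear growth a steeper slope implies a higher level at post. The Aim 3 curve starts once any treatment gap has already opened. From there, the slope describes what happens to the gap, not whether there is one.

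Parent strategy use is a primary outcome construct in Table 1, and Aim 3 is where lasting benefit is to be shown. A benefit that is simply maintained could be reported as no effect. One that fades in part, with treated parents still ahead, could be reported as a coefficient against the intervention.

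**Working it through.** **The plan's own figures.** The SAP gives 80% power at d = .61 and 90% at d = .71 with n = 86. It states no alpha, sidedness or allocation ratio. A two-sided 5% t-test with 43 per arm gives 79.8% and 90.2%, and 99.8% at the pilot d of 1.07. With 48 per arm, d = .58 and d = .67 give 80.3% and 90.1%. The figures reproduce. They concern a level difference, not the 3.1 slope.

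**Reading A: intervention predicts both intercept and slope.** The slope effect is (T24 gap − T7 gap) / time.
- Gain kept: zero.
- Gain partly fades, treated parents still ahead: negative.
- Gap widens after treatment ends: positive.

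The prediction is true in the first two cases. These signs do not depend on the variances.

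**Reading B: intervention predicts only the slope.** The T7 means are then forced equal across arms, and the expected coefficient is the slope difference − (V12/V11) × T7 gap. V11 is the variance of a fitted individual intercept, and V12 its covariance with the fitted slope. The size depends on the variances assumed below.

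**Assumptions (illustrative; not in the documents unless stated).** 43 per arm; 18 visits from T7 to T24, as in Table 1, with time scaled 0 to 1 (Sxx = 1.676); linear growth and complete data; total SD 1 at T7; residual variance .5, so var_I = .5; slope SD .5 over the period; intercept-slope correlation 0. The T7 gap is .61 SD, borrowed from the power section; it is not an estimate for parents. Ranges in brackets use residual variance .3 to .7, slope SD .3 to .8 and correlation −.4 to .4.

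**Standard errors, reading A.**
- Slope: √[2/43 × (.25 + .5/1.676)] = .160
- Mean level: √[2/43 × (.5 + .25/4 + 0 + .5/18)] = .166
- T24 level: √[2/43 × (.5 + .25 + 0 + .5 × (1/18 + .25/1.676))] = .199

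With gap g and fade f, the true contrasts are −g·f for the slope, g(1 − f/2) for the mean level and g(1 − f) for T24. Power comes from the noncentral t with 84 df.

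| T7 gap .61 | Slope sig. positive | Slope sig. negative | Mean level positive | T24 level positive |
|---|---|---|---|---|
| Kept | 2.5% | 2.5% | 95% (74% to >99%) | 86% |
| Halved | 0% | 47% (27% to 77%) | 78% (50% to 97%) | 33% |
| Fully faded | 0% | 97% | 44% (26% to 73%) | 2.5% |

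A 1.07 gap that fades fully still gives a positive mean-level test in 89%.

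For the slope test to have 80% power in favour of the prediction, the gap must widen by a further .45 SD (.32 to .63) after treatment stops, for example from .61 to 1.06.

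**Interval for the slope difference, reading A.** The half-width is 1.989 × .160 = .32 SD (.22 to .44). That is .32/.61 = 52% of a .61 gap (36% to 72%), but .32/1.07 = 30% of a 1.07 gap (21% to 41%).

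**Reading B, .61 gap kept.** V12 = 0 − .5 × .5/1.676 = −.149 and V11 = .5 + .5 × (1/18 + .25/1.676) = .602. The expected coefficient is (.149/.602) × .61 = +.15 SD. At correlation −.4, V12 = −.4 × √.5 × .5 − .149 = −.291, giving (.291/.602) × .61 = +.29 SD. With a 25% fade and correlation 0, it is −.1525 + .151, about zero.

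**The case against.** Four objections deserve an answer.

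1. *A growth curve with an intervention term normally includes the intercept.* The SAP defines the intercept as overall level, and for 3.2a it says "This will be accomplished by including intervention as a predictor in the child spoken word growth curve". If 3.1 is fitted that way, the T7, mean and T24 contrasts all follow from two fitted coefficients. This stands: the information would be available. What is missing is any statement that one of those contrasts decides the prediction.

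2. *Using more is simply how the SAP words parent slope outcomes.* Aim 1 follows the same pattern, so the contrast between the parent and child wording is weak evidence on its own. This also stands. The argument rests on the window starting after treatment.

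3. *Other analyses cover the level.* Analysis 1.1 shows whether a gain arose by T7, but its prediction is limited to the intervention period, and no joint reading with 3.1 is stated. The path from intervention to overall parent use in 4.2a and 4.2b comes closer. Yet Aim 4 is exploratory and conditional on an Aim 1 or Aim 3 effect, is not cited for this prediction, and leaves open whether the mediator is a level or a growth factor.

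4. *A mean-level test is not obviously right.* Correct: it can be positive when nothing remains at T24, as the last row of the table shows. The choice belongs to the sponsor.

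A reader might infer that 3.1 must come out null or negative whenever the gain is kept or fades, whatever model is fitted. The documents do not settle whether the intercept path is included, and under reading B a kept gain has a positive expected coefficient in the cases shown. Reading B is no defence, because its coefficient depends on nuisance variances.

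**Conclusion.** The point holds. The prediction concerns how much treated parents use the strategies after intervention, and the one analysis assigned to it names a parameter that does not answer that. With the intercept fitted, the slope is zero or negative in cases where the prediction is true. With only the slope fitted, it is a biased mixture of the T7 gap and later change. The signs under reading A follow from algebra; every percentage, and the size of the bias under reading B, rests on the assumed variances and gap.

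Two wider conclusions are not supported. A reader might infer that a non-significant slope can never exclude a large loss. Under the illustrative variances that is so for a .61 gap, where a zero estimate is compatible with losing about half, but not for a 1.07 gap, where losing half would be excluded. Nor is the whole of Aim 3 affected: 3.2a is worded as growth and matches its slope test, and 3.2b tests a score at follow-up. The defect is confined to 3.1. It should be fixed, but it does not call the design or the data collection into question.

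**What to change.** - In Analysis 3.1, state that intervention predicts both the intercept and the slope.
- Make a level contrast the test of the prediction: either the mean difference over T7-T24 (with linear growth, the intercept effect with time centred at the midpoint) or the T24 level difference (time centred at T24). The sponsor should name in advance which one decides.
- Always report the other level contrast beside it, and the slope difference with its confidence interval as the estimate of maintenance or fade.
- State the trade-off: the mean-level test has more power for a kept gain but can succeed with no advantage left at T24; the T24 test avoids that at a cost in power.
- In 3.2a keep the slope test and state that intervention also predicts the T7 intercept.

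The cost is SAP wording and a little modelling on data already planned; the 3.1 slope becomes a secondary result. If outcomes by arm have already been seen, the change must be disclosed as post hoc.

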The child's SLP and/or DTH will be consented separately. They will each complete separate video-taped sessions up to 2 times over the course of the child's participation in the study – around month 4 and when the child is 30 months old. After each session, the therapist will be asked to complete surveys. If the child is not receiving speech or developmental services in the home, or if the therapist does not consent to this research, the child and parent can still participate in this research study.

Table 1. Summary of assessments

Assessment	Description	Participant	Duration	Location	Time Point
Communication and Symbolic Behavior Scales (CSBS)	The child is presented with toys and activities designed to elicit prelinguistic communication. The interaction is video recorded and then scored.	Parent and Child	30 min.	Home or Lab	Pre (T0) Post (T7)
Preschool Language Scale - Fifth Edition (PLS-5)	The child is presented with different receptive and expressive tasks such as following simple directions and labeling pictures until the child provides an incorrect response to six consecutive items for both auditory comprehension and expressive communication subscales	Child	30 min.	Home or Lab	Pre (T0) Post (T7) Follow- up (T24)
Language Sample	The child plays with four different sets of toys and looks at a wordless picture book, while the parent engages with the child but does not talk.	Child	12 min.	Home or Lab	Pre (T0) Monthly
Parent-Child Interaction	The child and parent play "as they usually would" with a set of toys for 12 minutes.	Parent and Child	12 min.	Home or Lab	Pre (T0) Monthly
TELE-ASD-PEDS	Virtual screening assessment for autism, Parents will be offered this assessment if the parent or the clinical team has concerns the child may have autism during the regular course of the study. Parents will also have the opportunity to consent to this assessment at 36-months.	Parent and Child	35-60 min.	Home	At parent request or with parent consent at 36- months

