Parent Surveys (for children with hearing loss)	The MacArthur-Bates Communicative Development Inventories (MCDI): Words and Gestures or Words and Sentences (the parent selects which words their child says and understands out of 680 words). English, Spanish, and American Sign Language versions (if applicable) Use of Community-Based Intervention Services and Hearing Device Log (the parent answers questions about how many and what types of other therapy services their child received in the last month; indicates how often the child wears their hearing device across 8 different routines, such as meal times)	Parent	Surveys (90 mins)	Home	Pre (T0) Post (T7) Follow-up (T24)
	LittlEars Auditory Questionnaire (the parent				

Page 6 of 20

Revised: May 25, 2018

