After intervention (post), parents in the PICT condition will complete an intervention satisfaction survey. This measure has been used in previous studies of parent-implemented interventions and includes questions about how comfortable parents feels using the communication support strategies, their perceptions about their child's progress, and their rating of different parent instructional methods such as coaching and modeling. Participants assigned to the control group will not receive the PICT intervention. Participants in both groups will continue to receive early intervention services according to their Individualized Family Service Plan.

Participants will be asked if they would like to complete an additional, optional phase of the study around the time their child is 34-36 months old. At the 3rd DLEAT interview, parents will discuss the study with the lab manager and will be asked if they would like to participate. Participation would include an optional 1-hour appointment to complete the TELE-ASD-PEDS with research staff for \$50. If the research team has concerns, it will be recommended that a formal evaluation is scheduled in the participant's home state. This will help researchers understand more about social communication delays in deaf and hard of hearing populations.

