13.0 Audio/Video Recording

All testing and intervention sessions will be video recorded via a video platform (such as zoom) or on lab cameras if at the EIRG. All video and audio recordings will be stored on the [name] Lab server. These files will be stored by ID number. Hard copies and video cameras will be stored in a locked lab office until upload. Following upload to the server video files on the audio and video recorders will be deleted.

14.0 Potential Benefits to Participants:

Benefits to parents who participate in the intervention are expected to include: (a) improved strategies for working on their child's language and communication skills and (b) more accurate perceptions of the child's language and communication abilities. Parents have rated our training as helpful to them and their children and they have reported high levels of satisfaction with the training protocol. Parents in the control group will have the benefit of additional language development results. After each major assessment period at T0, T7, and T24 months, all parents will receive a comprehensive report describing their communication skills.

15.0 Risks to Participants:

Page 15 of 20 Revised: May 25, 2018

There are no obvious serious risks for any of the participants. The time involved in the study for families assigned to the PICT group is considerable; however, the perceived benefits outweigh the costs to families in personal time. Parents have rated our parent training as helpful to them and their children. The only potential risk to study participants associated with this project is the risk of confidentiality being violated. There are safeguards in place, as described below in section 16 to protect against breach of confidentiality. Given these safeguards, the likely impact of this risk of breach of confidentiality to participants is minimal. No risks to the participant's physical, psychological, social, cultural, financial, or legal risks are anticipated. Overall, the risks associated with this study are very low.

16.0 Provisions to Protect the Privacy and Confidentiality of Participants and the Research Data:

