The data will be monitored by the staff statistician and [name]. They will conduct the randomization, oversee data entry procedures, manage the database, train study staff on data entry procedures, and be responsible for maintaining the quality and integrity of the database as outlined below. Data entry will be completed using a centralized internet-based system (REDCap), which makes the project database instantly available to all authorized researchers in the system and permits access from any computer with an internet connection from multiple locations (via password protected logon). Summary reports (e.g., recruitment, assessment progress) can be generated immediately and are automatically updated with additional data. Reports can be created that document participant progress to-date and track missing data. These missing data reports will be reviewed weekly by the study team, such that we may try to acquire missing data in a timely manner (re-emailing or calling study participants to complete surveys; re-administering test items in the event that not all items were completed).

All data will be independently entered by two different research staff. Discrepancies between records will be automatically identified and verified. Additional quality assurance checks will be completed to check for missing data, range, and outliers. Once the data have been verified, they will be stored in a second "clean" dataset. Summary reports of the "clean" dataset will be organized by time point and measure. The "clean" dataset and summary reports will be reviewed quarterly by the independent biostatistician on the Data and Safety Monitoring Board. Outcomes by experimental condition assignment (intervention, control) will not be included in any interim reports.

Risks related to incorrect or biased scoring of measures will be minimized in the following ways. All standardized and observational measures will be conducted by independent observers and assessors naïve to the experimental condition. All testing sessions will be video recorded and procedural fidelity for test administration will be measured monthly to assess and ensure accuracy of test administration. Observers for all observational measures will be trained to point-by-point reliability of 90% for three consecutive administrations prior to coding the observational data. A second independent observer will code 20% of the observational measures. When reliability

Page 18 of 20 Revised: May 25, 2018

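### One of the two indicators in Analysis 3.2a is the MCDI, completed by unmasked parents, so an arm difference in reporting that changes over 18 to 36 months would be read as a difference in child word growth

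*SAP*

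**What the plan says.** - **Outcome.** SAP Analysis 3.2a: "Intervention will predict the slope factor in a latent growth curve model of child spoken language outcomes". The factor is "a latent variable of total number of different words said from the MCDI and total number of different spoken words from a language sample". SAP Table 1 gives the window as "18 to 36 months of age (18 time points between post and follow-up", so every occasion follows the training period. The same factor is the outcome in 4.2a and 4.3a.
- **Who reports.** Protocol Table 1 describes the MCDI as a checklist in which "the parent selects which words their child says and understands out of 680 words". It is repeated monthly as a parent survey.
- **Masking.** Parents cannot be masked: "Participants assigned to the control group will not receive the PICT intervention" (Protocol 8.0). The masking statement in Protocol 8.0 and 17.0 reads: "All standardized and observational measures will be conducted by independent observers and assessors naïve to the experimental condition". It does not extend to parent report.
- **Expected effect on the reporter.** Protocol 14.0 lists among the benefits for parents in the intervention "more accurate perceptions of the child's language and communication abilities".
- **The other indicator.** In the language sample the child plays "while the parent engages with the child but does not talk" (Protocol Table 1). It is video recorded and coded by masked observers.
- **Provision for method effects.** Under its data-reduction heading the SAP intends multi-trait multi-method and bifactor models where a construct spans several modes, parent report included. Analysis 3.2a does not say how this applies. It names no MCDI-specific factor, no test of equal measurement across arms and no single-indicator analysis.

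**The concern.** The intervention acts on the person who supplies one of the two indicators. If trained parents come to count words differently from untrained parents, part of the arm contrast in the MCDI is a change in the instrument. A model with one common factor and one arm effect on its slope cannot tell the two apart.

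3.2a is the growth test of the trial's long-term child outcome. The SAP overview also argues that, with all models in one framework, differing results can be attributed to constructs. A positive 3.2a beside a null PLS-5 result in 3.2b could then be read as an effect specific to vocabulary growth, when a drift in reporting would give the same pattern.

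**Working it through.** **Inputs from the documents.** 96 recruited and 86 after 10% attrition; growth-model power of 80% at d = .34 and 90% at d = .45 (SAP, Power Analysis).

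**Assumptions.** 1:1 allocation (43 to 48 per arm), two-sided alpha .05, no true effect, and the weights, correlations, vocabulary values and shift sizes below. None of these is given in the documents.

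**1. The plan's own figures.** Power = Φ(d·√(n/4) − 1.96). For n = 86 and d = .61: .61 × √21.5 = 2.83, power .807 (.798 by noncentral t; stated 80%). For d = .71: .909 (stated 90%). For n = 96, d = .58 gives .811 and d = .67 gives .907. These are reproduced and not disputed. The growth-model figures cannot be reproduced because the simulation inputs are not given.

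**2. Which reporting differences reach the slope.** Let true vocabulary be V(t) = i + s·t over 18 months, with s assumed to average 18 words per month (SD 9).
- Constant shift c in the trained arm: reported slope s, so the arm difference in slope is 0.
- Proportional shift k: reported slope (1 + k)s, so the difference is 18k words per month, or 18k/9 = 2k SD. An MCDI slope difference of .3 SD corresponds to k = 15%, and .5 SD to k = 25%.
- Shift c that fades to zero by 36 months: difference −c/18. For c = 40 this is −2.2 words per month, or −.25 SD.

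**3. Effect on the two-indicator outcome.** For an MCDI slope difference b (SD units), equal weights and slope correlation r, the spurious effect is (b/2)/√((1 + r)/2), tested against SE = √(2/n per arm): .216 for 43 and .204 for 48.
- b = .3: .15/√.85 = .16 (r = .7) to .15/√.75 = .17 (r = .5). False positives: 12% (43 per arm, r = .7) to 14% (48 per arm, r = .5).
- b = .5: .25/√.85 = .27 to .25/√.75 = .29. False positives: 24% to 29%.

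**4. Sensitivity to the standard error and weight.** The SAP's growth power implies SE = .34/2.80 = .121, or .45/3.24 = .139. (The two should agree if the standard error were constant: .45/.34 = 1.32 against an expected 1.157.) With the spurious effect taken as w·b and w = .5, b = .3 gives 23.5% or 19.1%, and b = .5 gives 54% or 43.7%. With SE .121 and b = .3, an MCDI weight of .3 gives 11.5% and a weight of .7 gives 40.9%. The SAP does not say what its growth-model d is scaled by, so these figures show only the range.

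**5. Simulation.** 3,000 trials per scenario, 43 per arm, least-squares slopes per child on an equally weighted composite. This stands in for the planned latent model, and the 680-word ceiling is not modelled.

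| Reporting shift in trained arm | Composite: false positives | Mean spurious effect (SD) |
|---|---|---|
| None | 5.5% | .00 |
| Constant, 20 / 60 words | 4.6% / 4.3% | .00 / .00 |
| Proportional, 5% / 10% | 5.5% / 7.6% | .05 / .10 |
| Proportional, 20% / 30% | 13.9% / 24.9% | .18 / .28 |
| Fading, 40 / 80 words | 8.2% / 20.9% | −.12 / −.25 |

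The language-sample slope alone rejects in 4.4% to 5.1% of trials in every scenario.

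**The case against.** **A reader might infer that any arm difference in reporting inflates 3.2a in favour of the intervention.** The documents do not support that. The tested parameter is a slope that starts after training ends. A stable difference goes to the intercept, and a fading one works against the intervention. Protocol 14.0 speaks of accuracy, which could raise or lower the reported count, and says nothing about divergence over the following 18 months.

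**A reader might also take the MCDI to be half of the outcome.** It is half by count of indicators. Loadings are estimated, so its weight may be more or less.

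**The SAP already foresees method effects.** With one indicator per method, method and trait cannot be separated at a single occasion, but 18 monthly occasions can carry an MCDI-specific factor. This stands in part. Such a factor removes an arm difference only if arm is allowed to predict it, and the SAP does not say so.

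**An assessor-based check exists.** The PLS-5 in 3.2b is given by a naïve assessor, though with parent assistance over video. It helps with spoken language at 36 months, but as a single score at that age it cannot confirm a claim about word growth.

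**The language sample is not wholly free of arm.** The parent is the silent play partner, and the intervention trains visual and interactive strategies. This stands: masked coding protects the count, not the interaction that produced it. Finally, 4.2a and 4.3a belong to an aim declared exploratory, so the consequence there is smaller.

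**Conclusion.** The concern holds in a limited form. As specified, 3.2a cannot distinguish an arm difference in word growth from an arm difference in MCDI reporting that changes over 18 to 36 months. The ambiguity runs both ways: a growing or proportional difference mimics benefit, and a fading one masks it. A constant difference does no harm.

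The 12% to 14% and 24% to 29% false-positive rates are conditional on assumed arm differences in MCDI slope of .3 and .5 SD, with no true effect, equal weights, a slope correlation of .5 to .7 and 43 to 48 per arm. They do not estimate what will happen in this trial, since the documents give no size or direction for the drift. The structural facts need no such assumption: an unmasked reporter, an intervention expected to alter that reporter's perception, and no safeguard written into 3.2a. They do not invalidate the analysis, but they justify an inexpensive pre-specified check on how a positive result may be described.

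**What to change.** Keep the two-indicator growth curve and add the following to Analysis 3.2a.

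(a) Fit the same growth model to the masked-coded language-sample word roots alone, and report its arm effect beside the MCDI-only slope, both in SD units. Describe a positive 3.2a as language growth, rather than possible reporting change, only if the language-sample slope agrees in direction and approximate size.

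(b) Make the multi-method provision explicit: an MCDI-specific growth factor with its own level and slope, both predicted by arm, with the language sample as reference. A single time-constant path from arm to the MCDI is not enough. It absorbs the level difference, which was harmless, and leaves the slope bias in place. The arm effect on the MCDI-specific slope should be reported as a possible reporting shift, since it could also contain words used at home that a 12-minute sample misses.

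Apply the same check to 4.2a and 4.3a.

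The cost is two or three extra model fits on data already collected. The single-indicator curve is less precise. So is the common-slope arm effect in (b), because it then rests largely on the language sample; the loss is not quantified here. The play-partner limitation should be stated alongside the result.
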